8.3. Exploratory analyses

Preliminary to the main analyses, the data will be checked for obvious errors that cause outliers and for systematic errors due to improper coding at one or a few centers. For each *time x trt* cell, the distribution of outcome values will be summarized by its mean, standard deviation, and five number summary. Boxplots of the cell-specific distributions will be made to see the basic patterns of change over time and to detect outlying values. The autocorrelation matrix of repeated measures on the individual will be estimated separately for each treatment group.

After the main analyses, numerous exploratory analyses will be conducted using variants of the model above to generate hypotheses for future research.

8.4. Subgroups of interest

We will quantify the evidence in the study data in support of the possibility that the treatment effect differs between persons with ($Z=1$) versus those without ($Z=0$) pre-specified characteristics. Subgroups of interest include: Current vs. Former smokers; severe emphysema ($\text{pct950} > 15$) vs mild emphysema ($\text{pct950} < 15$); severity of airflow limitation ($\text{FEV}_1 < 50\%$ predicted vs $\text{FEV}_1 > 50\%$ predicted); and men vs women. In addition, other baseline characteristics may be explored. The model above will be extended to include the variables Z

*and Z*trt*. The coefficient for the 2-way interaction is the difference in the treatment group effects (losartan vs placebo) between the Z=1 and Z=0 subgroups. We will reject the null of no difference in treatment effects between the subgroups if the 95% confidence interval for this 3-way interaction coefficient excludes 0.

Other subgroups may be identified post hoc. The same model can be used to quantify the evidence for a difference in treatment effect for these subgroups. However, we view such analyses as hypothesis generating, not hypothesis testing.

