2.3. Trial design /Schema

The trial is a parallel, randomized, placebo-controlled trial with two treatment groups, losartan at 100 mg/day and placebo. Participants will be randomly assigned in equal allocation to one of two treatments. The treatment period is 48 weeks with follow-up visits at 12-week intervals. Participants assigned to losartan will start with a dose of 50 mg/day; participants assigned to placebo will start with one capsule per day. A titration visit will be done at 2 weeks; if the systolic BP is >90 mm Hg and the diastolic BP is >60 mm Hg, the drug dose will be increased to 100 mg per day or matching placebo will be increased to two capsules per day. Symptoms, lung function, and specimens are collected at baseline and select follow-up visits. HRCT will be done at baseline and 48 weeks.

[figure not shown]

Figure 1: LEEP Trial design - schema

PFT: Pulmonary Function Test; HRCT: High Resolution Computed Tomography

3. Eligibility criteria

Participants with mild to severe COPD will be screened using the criteria below. Participants will be asked to sign informed consent before any screening procedures are performed.

3.1. Inclusion criteria:

- Age of 40 years or older at V1, either gender
- Mild to severe COPD (post-BD FEV₁/FVC ratio \leq 0.70 and FEV₁ 20-80% predicted) at V1
- Current or former smoker (\geq 10 pack-year history at V1)
- HRCT Scan with 5-35% of voxels with density $<$ -950 Hounsfield Units (HU) at V1
- Ability to understand and willingness to sign consent documents

3.2. Exclusion criteria:

- Current therapy with angiotensin converting enzyme (ACE) inhibitor or angiotensin receptor blocker (ARB)
- Known intolerance to ACE inhibitor or ARB
- History of angioedema
- Conventional indication for ACE inhibitor or ARB (including history of myocardial infarction, known cardiomyopathy)
- Renal insufficiency (GFR $<$ 30 mL/min by Cockcroft-Gault calculation)
- Current regular use of NSAIDs defined as daily use 5 or more days of the week for more than one month
- Current treatment with a potassium sparing diuretic
- Potassium supplementation or serum potassium level of \geq 5.0 mEq/L at V1
- COPD exacerbation requiring treatment within 6 weeks at V1
- Chronic systemic corticosteroid use $>$ 10mg/day of prednisone
- Resting SpO₂ $<$ 89% on 2L nasal cannula continuous flow; unless at altitude $>$ 4,000 feet, then resting SpO₂ $<$ 89% on 4L NC continuous flow

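### Section 8.4 tests effect modification by baseline pct950 and FEV1 % predicted only through two-group cuts, which costs power if modification is roughly linear; continuous interaction terms would be a cheap improvement

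*Combined protocol and SAP*

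**What the plan says.** Section 8.4 defines each modifier as a two-level variable, comparing "persons with ($Z=1$) versus those without ($Z=0$) pre-specified characteristics". The list begins "Subgroups of interest include: Current vs. Former smokers; severe emphysema". For pct950 the groups are above 15 and below 15. For "severity of airflow limitation" they are FEV1 below 50% and above 50% predicted. The primary model is extended by Z and Z×trt, and the decision rests on that one coefficient: "We will reject the null of no difference in treatment effects between the subgroups if the 95% confidence interval" for it excludes zero. The section first calls the coefficient a 2-way interaction, but the rule then reads "3-way interaction coefficient excludes 0".

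Both variables are collected over wide ranges. Section 3.1 admits "HRCT Scan with 5-35% of voxels with density" below -950 HU, and FEV1 of 20-80% predicted. Section 8.1 already carries baseline pct950 as a continuous covariate, but only as a main effect. No section commits to a continuous modifier-by-treatment term. The nearest openings are the unspecified exploratory variants in Section 8.3 and the remark in Section 8.4 that further baseline characteristics may be looked at.

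**The concern.** Exploring heterogeneity of treatment effect is one of the four aims in Section 2.2. Section 8.4 gives the pre-specified subgroups a formal rejection rule and reserves the hypothesis-generating label for post hoc ones, so these tests are more than a display.

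They are also imprecise from the start, because Section 8.5 sizes the trial for the main effect alone. A two-group cut treats a participant with pct950 of 16 like one with 34, and separates 14 from 16 completely. Where the effect changes gradually, that gives up power the trial can ill spare, although the continuous values are already in the dataset.

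**Working it through.** **The plan's own figure.** The documents give no power or sample size for the interaction tests. The related figure in Section 8.5 is for the main effect: delta 2, SD 4, two-sided alpha 0.05, power 90%. The two-sample formula gives 2 × 16 × (1.960 + 1.282)² / 4 = 84.1 per group, or 86 with the t-distribution. The stated 88 gives 91.3% power, and 88 / (1 − 0.20) = 110. The figure is reproduced closely, but it says nothing about interactions.

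**Precision of a binary interaction.** With SD 4 and 220 participants in two equal subgroups, there are 55 per cell:
- SE = √(4 × 16 / 55) = 1.08.
- Difference detectable with 80% power = (1.960 + 0.842) × 1.08 = 3.0 points. With 176 participants it is 3.4.
- Both exceed the plan's minimally important difference of 2 for the treatment effect itself.

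**Information kept by the cut.** If modification is linear in X and treatment is independent of X, the efficiency of the Z×trt test relative to the X×trt test is corr(X, Z)². For X uniform and cut at fraction c of its range, this equals 3c(1 − c).
- pct950: c = (15 − 5) / (35 − 5) = 1/3, so 3 × 1/3 × 2/3 = 0.667. The loss is 33%, as if 147 of 220 participants were used.
- FEV1: c = (50 − 20) / (80 − 20) = 1/2, so 3 × 1/2 × 1/2 = 0.750. The loss is 25%, as if 165 of 220 were used.

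**Effect on power.** Take as reference a continuous test with 80% power (non-centrality 2.80). Power after the cut is Φ(2.80 × √efficiency − 1.96).
- pct950: Φ(2.80 × 0.816 − 1.96) = 63%.
- FEV1: Φ(2.80 × 0.866 − 1.96) = 68%.
- Simulation (n = 220, SD 4, 4,000 runs) gave 79% falling to 61%, and 79% falling to 66%.

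**Sensitivity to the assumed distribution**, truncated to the eligible range:

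| Modifier | Assumed shape | Loss |
|---|---|---|
| pct950 | right-skewed (exponential), mean 11 to 15 | 29-33% |
| pct950 | normal, mean 13 to 17 | 32-35% |
| pct950 | normal, mean 19 to 20 | 40-44% |
| FEV1 | normal centred at 50 | 33-36% |
| FEV1 | normal off-centre, mean 42 to 59 | 34-45% |

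At a 45% loss (efficiency 0.55), the 80% reference falls to about 55%.

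**Boundary values.** The named groups use strict inequalities on both sides, so exactly 15 and exactly 50 fall in neither. The documents do not state the recording precision. If FEV1 % predicted were a whole number, the expected count at 50 is 220 / 61 ≈ 4 (uniform), or about 7 (normal, mean 50, SD 12). For pct950 recorded to 0.1, it is 220 × 0.1 / 30 = 0.7, so fewer than one participant. Rounded to a whole number, it is 220 / 31 ≈ 7.

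**The case against.** The strongest reply is that the loss depends on the form of modification. Squared correlation is symmetric. If the effect really stepped at 15, the linear term would be the one keeping only 67%, and a simulation of that case (uniform pct950, n = 220) gave 79% power for the binary test against 60% for the linear one. The documents do not say which form holds. This stands, and it is why the loss must be stated conditionally. A reader might infer that the plan certainly discards a quarter to a third of the information. The documents do not support that, since they give neither the shape of modification nor the baseline distributions. Equally, nothing in them suggests a step at either cut.

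Second, 80% power is a favourable reference. For a 1-point difference between equal subgroups, binary power is Φ(1 / 1.08 − 1.96), about 15%. A linear FEV1 test at 0.75 efficiency would have Φ(1 / (1.08 × √0.75) − 1.96), about 19%. Both are inconclusive. This also stands: the gain is real only for fairly large modification.

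Third, a contrast between named severity groups answers the aim directly and is easier to read than a slope, and Section 8.3 leaves room for a continuous analysis. The first part is a good reason to keep the groups on display. The second shows that a continuous test is permitted, not that it is planned.

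A reader might also infer that participants at the boundary will be dropped, or that the tested coefficient is undefined. Neither follows. The with/without framing could place a boundary value in Z = 0, although the named groups do not say so. The sentence before the rule identifies the coefficient as the difference in treatment effect between the two levels of Z.

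**Conclusion.** The point holds as a low-severity, low-cost improvement. Section 8.4 plans only dichotomised interaction tests for two continuous modifiers. If modification is roughly linear and baseline values are spread uniformly over the eligible ranges, this loses about 33% of the information for pct950 and 25% for FEV1, taking an 80% power test to about 63% and 68%. Other plausible shapes put the loss at roughly 29-45%. With a true step at the cut there is no loss, and a linear test would do worse. No primary or secondary treatment comparison depends on this. The unassigned boundary values and the interaction-order slip are editorial and would not merit a comment by themselves.

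**What to change.** In Section 8.4, before unblinding:
- Pre-specify the continuous pct950×trt and FEV1 % predicted×trt terms as the interaction tests for these two modifiers.
- Report the estimated treatment effect with its 95% CI at chosen values, such as the quartiles of each modifier.
- Keep the estimates for the groups cut at 15 and 50% as the accompanying display, with ≥ on one side so that every participant is assigned.
- Change 3-way to 2-way in the decision rule.

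The cost is a change of wording and a few lines of analysis code, with no new data and no change to the primary analysis. The downside is a linearity assumption. A spline can check it, but that check has low power at n = 220 and should be described as supportive only.

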2.2. Study aims

- To measure the effect of losartan on HRCT-measured emphysema progression at 48 weeks
- To measure the effect of losartan on lung function (spirometry and HRCT-measured lung volumes)
- To explore sub-groups of interest for heterogeneity of treatment effects
- To determine the safety and tolerability of losartan in emphysema patients

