8.1. Primary analysis

The primary goal of analysis is to precisely estimate the difference in response between the losartan and placebo groups by comparing between-group means of changes from baseline pct950 over the time course of treatment. The secondary goals require estimation of analogous differences in response trajectories separately for each secondary response variable. For analytic methods, we propose a series of generalized linear mixed models (GLMMs) for responses (Y) with possibly g -transformed) expected primary or secondary responses, $g(E(Y_{ij}|b_{0i}, \beta_i X_{ij}))$, where 1.) $(\beta_0 + b_{0i})$ for the i^{th} patient response is a random intercept (to account for serial correlations in the within-patient responses) with fixed mean β_0 and random normal distributed offsets b_{0i} , with mean zero and standard deviation $\sigma_{b_{0i}}$ and 2.) X_{ij} are fixed values of j^{th} covariate for the i^{th} patient and β_i is the fixed unknown regression coefficient to be estimated for covariate X_j . Covariates will include site (14 binary spline indicator variables for the 15 category site stratification), baseline values of the Y response, an indicator variable for treatment group ($trt = 1$ losartan, 0 placebo), and either spline indicators for time or a continuous function for the fixed time trend in mean response, and, if needed, interaction terms between the time covariates and the (trt) treatment group indicator. The primary outcome is change in pct950 from baseline after 48 weeks of treatment ($Y = \text{pct950} - \text{pct950}_{b_i}$) and $g(\cdot)$ is the identity function, so the above model simplifies to $Y_i + \varepsilon_i = E(Y_i | b_{0i}, X_i) = \beta_0 + b_{0i} + \beta_1 trt + \beta_2 \text{pct950}_{b_i} + \{\beta_j X_{ij}\} + \varepsilon_{ij}$, where β_0 is the intercept for the fixed effects, b_{0i} is the normal $(0, \sigma_{b_{0i}})$ random intercept offset for each participant, β_1 is the primary losartan vs placebo treatment effect = mean difference in 48 week change in pct950 from baseline, losartan vs. placebo, $\{\beta_j\}$ is the set of regression coefficients to account for stratification by site, and ε_i is a normal $(0, \sigma^2)$ random error for the i^{th} change from baseline in pct950. The primary analysis will focus on β_1 , = mean losartan vs. placebo mean change over 48 weeks in pct950. We will estimate a 95% confidence interval for the losartan vs placebo mean difference, β_1 , using the regression estimate and the t -distribution; we will reject the null that losartan is equivalent to placebo if the 95% interval excludes 0.0. A robust variance estimate³⁷ will be used to guard against incorrect inferences due to misspecification of the assumed serial correlation structure among repeated observations on each subject.

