8.2. Secondary analyses

As indicated above, the same basic model specified above can be used for the secondary outcomes, most of which are continuous. For a binary secondary outcome, we will use the logistic regression analog in which $g()$ above is the logistic function, $g(u)=\log\{u/(1-u)\}$. Since the strict interpretation of odds ratios from mixed models with the logistic link is dependent on the value of the random effect variable (participant), we will also use maximum likelihood estimation and robust variance estimation described for the primary analysis above. The same assumptions and methods for missing data for the primary outcome will also be used in the secondary analyses.

In particular, we seek to estimate the treatment effect for each of 5 lobes of the lung. A simple approach is to use the basic change-from-baseline model described above separately for data from each lobe and then use a gate-keeper Chi-square test and Bonferroni correction to account for the multiplicity of tests. This method, while valid, does not provide evidence about the correlation among the estimates from the 5 lobes that is itself of scientific interest. Therefore, we will use a multivariate version of the GLMM from Section 8.1 that simultaneously estimates the treatment effect for the 5 lobes and produces both the 5 estimates of treatment effect as well as their covariance matrix³⁸. We will use these results to conduct gate-keeper Chi-square test of the null hypothesis that the 5 treatment effects are all the same across lobes and if this null is rejected, provide lobe-specific treatment effect estimates with 99% Bonferroni-corrected confidence limits to ensure that the joint coverage probability is 95%. In addition, we will also show estimates and 95% confidence limits for the between lobes correlations.

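### Section 8.4 rests its subgroup rule on a 3-way coefficient that its model does not contain, and states formal rejection at 5% for four factors that Aim 3 calls exploratory

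*Combined protocol and SAP*

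**What the plan says.** Section 8.4 names four pre-specified subgroup factors: smoking status (current or former), emphysema severity (pct950 cut at 15), airflow limitation (FEV1 cut at 50% predicted) and sex. It adds that other baseline characteristics may be explored.

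On the model: "The model above will be extended to include the variables Z". The product Z×trt is the only other term added. On the meaning: "The coefficient for the 2-way interaction is the difference in the treatment group effects (losartan vs placebo) between the Z=1 and Z=0 subgroups".

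On the decision, the plan commits itself as follows: "We will reject the null of no difference in treatment effects between the subgroups". The condition that it attaches to this step reads: "if the 95% confidence interval for this 3-way interaction coefficient excludes 0".

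The section ends by classing subgroups found post hoc as hypothesis generating rather than hypothesis testing. It does not say this of the four named factors.

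Three other places bear on the point:

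- Section 2.2, third aim: "To explore sub-groups of interest for heterogeneity of treatment effects".
- Section 8.1, the model being extended: "The primary outcome is change in pct950 from baseline after 48 weeks of treatment". In its simplified form it contains treatment, baseline pct950 and site, with no time term.
- Section 8.2, lobe analyses: after a gate-keeper test, "99% Bonferroni-corrected confidence limits to ensure that the joint coverage probability is 95" percent.

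**The concern.** There are two separate problems in the same few lines.

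First, the coefficient that carries the decision is not the one that the model defines. The definition is 2-way and the rule is 3-way. A pre-specified rule should identify its test statistic without interpretation, above all where more than one candidate could be fitted.

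Second, the plan does not settle what kind of evidence these tests provide. Aim 3 says explore. Section 8.4 says reject, and keeps the hypothesis-generating label for post hoc findings, so by contrast the four named factors read as hypothesis tests. No allowance is made for testing four of them, although section 8.2 does allow for five lobes.

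What is at stake is a subgroup claim. A null that has been formally rejected on a pre-specified factor could be reported as showing that losartan works differently in, say, current and former smokers, when an uncorrected set of four tests produces such a result fairly often by chance. Section 1.4 shows that such results carry weight here: part of the rationale for this trial is a subgroup finding from the proof-of-concept study (p = 0.06).

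**Working it through.** **Which coefficient can be tested**

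- pct950: sections 2.3 and 7.1 provide two scans, at baseline and at week 48. Each participant has one change score, so there is no time factor and no Z×trt×time term. The only interaction in the extended model is Z×trt.
- Spirometry: the schedule in section 4.1 has two post-baseline visits (weeks 24 and 48).
- SGRQ-C, mMRC, CAT and PROMIS-20a: four post-baseline visits (weeks 12, 24, 36 and 48).
- Section 8.1 allows time-by-treatment terms if needed, and section 8.2 reuses the model for secondary outcomes. If section 8.4 were applied there, Z×trt and Z×trt×time could both be fitted. Whether they test the same thing depends on the coding of time. If the treatment effect is a difference in slope, the 3-way term is the effect modification. If the effect is a difference at week 48 or averaged over visits, it is not.

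**Chance of a false rejection**

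The plan states no family-wise error for the subgroup tests, so there is no figure of its own to reproduce. The lobe figure in section 8.2 does reproduce: 1 − 0.05/5 = 0.99, that is 99% limits.

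Inputs from section 8.4: four factors, each tested with a 95% interval (two-sided alpha 0.05). Assumptions: one outcome and no true effect modification for any factor.

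- Independent tests: 1 − 0.95⁴ = 1 − 0.8145 = 0.1855, or 18.5%.
- Ceiling whatever the correlation: 4 × 0.05 = 20%.

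The documents give no correlations between the tests, so a range was assumed and simulated with normal test statistics:

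| Assumed correlation | At least one false rejection |
|---|---|
| Emphysema and FEV1 tests only: 0.3 / 0.5 / 0.7 | 18.3% / 18.0% / 17.3% |
| All four equally: 0.1 / 0.2 / 0.3 / 0.5 | 18.4% / 18.0% / 17.4% / 15.6% |

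A simulation of whole trials (220 participants, SD 4, each factor splitting the sample evenly, four separate models with trt, Z and Z×trt, 8,000 runs) gave 18.9%, 18.3% and 18.7% for underlying correlations of 0, 0.5 and 0.7 between emphysema and FEV1. Simulation error is about √(0.185 × 0.815/8000) = 0.4 percentage points, so these three do not differ meaningfully.

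Four is the minimum count. If further baseline factors were tested under the same rule, the independence figure would be 1 − 0.95⁵ = 22.6% for five and 1 − 0.95⁶ = 26.5% for six.

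**What a correction would do**

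- Bonferroni level: 0.05/4 = 0.0125, that is 98.75% intervals. Family-wise error if independent: 1 − 0.9875⁴ = 4.9%, and at most 5% in any case.
- Interval width: 2.498/1.960 = 1.27, so 27% wider.
- Power, with 110 per group and SD 4 (section 8.5), and assuming a 50:50 split and an interaction of 2 points: SE = 4 × √[(2/110) × (1/0.5 + 1/0.5)] = 1.079, and 2/1.079 = 1.854. At alpha 0.05 power is Φ(1.854 − 1.960) = 46%. At 0.0125 it is Φ(1.854 − 2.498) = 26%.

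**The case against.** The best defence of the text is that nobody would be misled. The sentence refers back with the word this, the only interaction just defined is Z×trt, and the null as stated is equality of treatment effects between subgroups. For pct950 that defence stands: a reader might infer that the rule cannot be carried out, but model, estimand and null all point to one coefficient and an analyst would almost certainly test it. It is weaker for repeated outcomes, where a 3-way term could be fitted, although section 8.4 does not expressly extend the rule to them.

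On multiplicity, the defence is that subgroup work is exploratory by aim, the factors are few and named in advance, and the plan tests interactions rather than effects within each subgroup, which is already the more cautious method. All of this is fair. Nowhere do the documents call these tests confirmatory, and no efficacy conclusion depends on them. What it does not answer is the rejection sentence and the reservation of the hypothesis-generating label for post hoc subgroups.

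A reader might also infer from section 8.2 that consistency requires Bonferroni here. The parallel is loose. The lobe procedure first tests whether effects are equal across lobes, and then sets joint coverage for five treatment-effect estimates. It is not a family of interaction tests, and 98.75% intervals without a gate-keeper would not match it.

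**Conclusion.** The point holds as a defect of specification. The decision rule names a coefficient that the stated model lacks, probably through a slip, and the section attaches formal rejection to work that the aims call exploratory.

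The size is an 18.5% chance of at least one false rejection among the four named factors. It assumes independent tests, one outcome and no true effect modification. Assumed correlations give about 16% to 19%, and 20% is the upper limit.

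That figure should not be read as the trial's false-positive rate. The primary test of losartan against placebo is a single comparison at 5%, and nothing in section 8.4 changes its type I error. Nor do the documents support saying that the plan must correct for multiplicity: that follows only if the rejection claims are kept.

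**What to change.** In section 8.4:

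1. Replace *this 3-way interaction coefficient* with *the Z×trt coefficient for the week-48 change*. This settles pct950 and also fixes the contrast for any repeatedly measured outcome to which the rule is applied.
2. Remove the sentence that rejects the null. State instead that the four interaction estimates will be reported with unadjusted 95% intervals and labelled exploratory, in line with Aim 3.

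This costs only wording. Data collection, sample size and the precision of the estimates stay the same; what is given up is the right to a formal subgroup claim.

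If the sponsor wants to keep formal rejection for the four factors, the tests need multiplicity control, for example 98.75% intervals. The price is intervals 27% wider and, under the assumptions above, power for a 2-point interaction falling from about 46% to about 26%. With power that low even before correction, the exploratory option fits the design better.
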